4 POPULATIONS FOR ANALYSIS

4.1 Full Analysis Population

The full analysis population is defined as all subjects who are enrolled in this study.

4.2 Safety Population

The safety population is defined as all subjects who are enrolled and received at least one dose of roflumilast in the parent study or at least one confirmed dose of roflumilast in this study.

 Innovaderm Research	STATISTICAL ANALYSIS PLAN, Final Version 1.0
Protocol Number: ARQ-151-313	Sponsor: Arcutis Biotherapeutics, Inc.

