5.1.2. Contraception Requirements

Females of childbearing potential (FOCBP) must have a negative urine pregnancy test at Day 1 of study ARQ-151-313. In addition, sexually active FOCBP must agree to use at least one form of a highly effective or barrier method of contraception throughout the trial according to Contraception Requirements (Figure 1).

Figure 1: Contraception Requirements for Female Subjects

¹Subjects using hormonal contraceptives must have been on a stable dose for at least 4 weeks before Day 1.

²The above list of contraceptive methods does not apply to subjects who are abstinent for at least 4 weeks before Day 1 and will continue to be abstinent from penile-vaginal intercourse throughout the study. The reliability of sexual abstinence needs to be evaluated in relation to the duration of the clinical trial and the preferred and usual lifestyle of the participant.

³Female condom and male condom should not be used together.

5.1.3. Day 1

Enrollment will take place at the Day 1 visit after the subject has been found to be fully eligible for participation. A subject will be considered enrolled into the study upon the first IP application.

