6.3. Subjects to Analyze

The safety populations are defined as all subjects who are enrolled and received at least one confirmed dose of study medication.

Pharmacokinetic Population (PK): The PK population includes all subjects receiving active drug and had a PK draw (concentration data available) post-baseline. This population will be used for the analysis of PK concentrations.

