1 INTRODUCTION

This Statistical Analysis Plan (SAP) describes the planned analysis and reporting for Arcutis Biotherapeutics, Inc. clinical protocol ARQ-151-313. The analyses described in the SAP are based upon the protocol Amendment 1 dated 17 September 2021. In case of changes (note that any such changes are described in section 3.6 below) between the protocol and the SAP, the SAP will be used to guide the statistical analysis. Deviations from the SAP are not expected. If any, they will be described and justified in the final Clinical Study Report (CSR), as appropriate.

This version of SAP has been developed and finalized prior to ARQ-151-313 database lock for the first Interim Analysis (IA).

Each IA will be performed only after the following steps have been completed: approval of this SAP, clinical trial data up to a pre-specified data cut-off date are entered into the database for subjects from parent studies ARQ-151-311 and ARQ-151-312 and any discrepancies in the data are resolved, finalization of the classification as important or non-important of each protocol deviation that occurred before or on the pre-specified data cut-off date for subjects from parent studies ARQ-151-311 and ARQ-151-312, and the database is locked. That is, subjects from parent study ARQ-151-315 will not be included in the IAs.

Similarly, the final analysis will be performed only after the following steps have been completed: approval of this SAP, clinical trial data are entered into the database for all subjects and any discrepancies in the data are resolved, finalization of the classification as important or non-important of each protocol deviation, and the database is locked.

ARQ-151 Cream 0.15% and ARQ-151 Cream 0.05% will be described as “roflumilast cream 0.15%” and “roflumilast cream 0.05%” throughout this document and the tables, listings, and figures (TLFs).

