3.6 Changes to the Analysis from the Protocol

Rationale for change	Description of the change
A categorical summary of amount of investigational product used by each subject based on tube weights was excluded from the SAP as it was determined that it was not necessary.	
Original text:
 
The amount of investigational product used by each subject based on tube weight will be summarized by treatment using descriptive statistics, and categorically.
 
Changed to:
 
The amount of investigational product used by each subject based on tube weight will be summarized by treatment using descriptive statistics.

Analyses to be performed by cohorts (i.e., 24 vs. 52 weeks) were excluded from the SAP as it was determined that it was not necessary.	
Original text:
 
The analysis will be performed by cohorts and overall over time.
 
Changed to:

 Innovaderm Research	STATISTICAL ANALYSIS PLAN, Final Version 1.0
Protocol Number: ARQ-151-313	Sponsor: Arcutis Biotherapeutics, Inc.

Rationale for change	Description of the change
Update compliant criteria for subject who are on BIW dosing schedule.	
For analysis purposes, the TLFs will be summarized overall and by previous treatment group in the parent studies.
 
Subgroup analyses by Cohort will be performed for specific endpoints (refer to Section 6.6)

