5.2 Baseline

There are two baseline definitions for the analyses:

- Primary baseline is defined as the last observation before or on the first dose of roflumilast cream 0.15% or 0.05% in ARQ-151 parent studies for subjects administered roflumilast previously and before or on the first dose of roflumilast cream 0.15% or 0.05% in this study* for subjects administered vehicle previously.
- OLE baseline is defined as the last observation before or on the first dose of roflumilast cream 0.15% or 0.05%* in this study.

If the last non-missing assessment was performed on the same date as the first dose of roflumilast cream* and time is not available, the assessment will be considered as baseline, except for adverse events (AEs) and medications starting on the first dose date which will be considered post-baseline. For subject local tolerability assessments, if the last non-missing assessment was performed on the same date as the first dose of roflumilast cream*, the assessment will be considered as baseline, regardless of the time of the assessment.

For the subjects administered vehicle in the parent study, the definition for Primary and OLE baselines are the same.

* Enrollment date (usually the Week 4 visit in the parent study) for enrolled subjects who discontinued early from this study before the first application of roflumilast cream 0.15% or 0.05%.

The following table ([Table 2](#)) described the baseline used in the analysis:

 Innovaderm Research	STATISTICAL ANALYSIS PLAN, Final Version 1.0
Protocol Number: ARQ-151-313	Sponsor: Arcutis Biotherapeutics, Inc.

Table 2 Summary of Primary/OLE Baseline in the Analyses

Analyses	Baseline*
Demographics and Baseline Characteristics	Primary baseline and OLE baseline, as applicable
Efficacy Analysis	Primary baseline and OLE baseline
Safety analysis for AEs and concomitant medications	OLE baseline
Safety analysis for clinical laboratory, vital signs, local tolerability assessments. PHQ-8, Modified PHQ-A, CDI-2, C-SSRS, and physical examination	Primary baseline

* Refer to Section 8 for more details.

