6.2.1 Multiple Imputation

For the vIGA-AD secondary efficacy endpoints (refer to Section 12.2), vIGA-AD non-imputed values collected during the parent studies and this study (including the last available data of subjects who prematurely withdraws from this study) will be appended together after having been assigned to pre-specified analysis visit using the analysis windows defined in their respective study (parent study SAPs or this SAP Section 5.4, as applicable). Doing so, each subject will have between 4 (subjects who enrolled in OLE and discontinued early before the first application of

 Innovaderm Research	STATISTICAL ANALYSIS PLAN, Final Version 1.0
Protocol Number: ARQ-151-313	Sponsor: Arcutis Biotherapeutics, Inc.

roflumilast cream during the OLE study) to 7 (subjects in Cohort-Week 24 who completed the OLE) or 9 (subjects in Cohort-Week 52 who completed the OLE) vIGA-AD non-imputed values:

OLE Analysis Visit	Study/Analysis Visit
OLE Week -4	Parent study derived baseline value (refer to parent study Section 5.2)
OLE Week -3	Parent study / analysis visit Week 1
OLE Week -2	Parent study / analysis visit Week 2
OLE Day 1	Parent Study / analysis visit Week 4
OLE Week 4	OLE study / analysis visit Week 4
OLE Week 12	OLE study / analysis visit Week 12
OLE Week 24	OLE study / analysis visit Week 24
OLE Week 36*	OLE study / analysis visit Week 36
OLE Week 52*	OLE study / analysis visit Week 52

* Cohort-Week 52 subjects only.

Note: No missing data are expected for the OLE Week -4 to OLE Day 1 analysis visits since subjects must have completed a parent study to be eligible for enrollment in this OLE study.

Then, to comply with the definition of the parent studies' primary estimand (refer to parent studies Section 12.1.1), efficacy data assigned to a pre-specified analysis visit will be removed from the source data used for the multiple imputation process if subject's last dose day falls within the analysis visit window or is prior to the start of the analysis visit window used to assign data to a pre-specified analysis visit (refer to Section 12.2) for subjects who discontinued due to lack of efficacy or adverse event. This procedure will ensure that the data collected on or after intercurrent events are not used in the imputation process.

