13 SAFETY ANALYSES

Safety analyses will be conducted using the safety population. No p-values or confidence intervals will be provided for safety endpoints, with the exception of EAIRs (refer to Section 5.5) which will be accompanied by 95% CIs.

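### SAP 4.2 admits former-roflumilast subjects never dosed in the extension to the TEAE denominator but not their former-vehicle counterparts; the dilution is small and avoidable.

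*SAP*

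**What the plan says.** Protocol 6.3 states: "The safety populations are defined as all subjects who are enrolled and received at least one confirmed dose of study medication". The protocol synopsis gives the same rule.

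SAP 4.2 keeps the enrolment condition but offers two routes into the population. The subject must have "received at least one dose of roflumilast in the parent study or at least one confirmed dose of roflumilast in this study". SAP 13 then says: "Safety analyses will be conducted using the safety population". SAP Appendix 1 makes the denominator of each percentage the population count in that treatment group, unless stated otherwise.

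SAP 1 lets the SAP guide the analysis where it differs from the protocol, and says of such changes: "note that any such changes are described in section 3.6 below". Three rationales can be read in SAP 3.6. They concern tube-weight categories, by-cohort analyses and compliance on twice-weekly dosing ("Update compliant criteria for subject who are on BIW dosing schedule"). None concerns the safety population.

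The two documents also use the word *enrolled* differently. Protocol 5.1.3 says: "A subject will be considered enrolled into the study upon the first IP application". SAP 5.2 has a special rule "for enrolled subjects who discontinued early from this study before the first application of roflumilast cream 0.15% or 0.05" percent, SAP 5.3 repeats it for study day, and SAP 6.2.1 counts the data of "subjects who enrolled in OLE and discontinued early before the first application of" roflumilast cream in the extension.

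**The concern.** SAP 13.1 ties treatment emergence to the OLE: the event must start after the Day 1 application in ARQ-151-313, or be present at treatment initiation and worsen during treatment. A subject who never applied the cream in the OLE cannot meet that definition. Protocol 5.1.12 also starts the recording of non-serious events only at the first application. Such a subject can add to a TEAE denominator but not to the numerator.

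SAP 4.2 does this on one side only. A never-dosed subject from a roflumilast parent arm enters through the parent-study route, while a never-dosed subject from a vehicle arm has no route in. TEAEs and SAEs are the primary endpoints, and they are tabulated by former treatment. The two columns would therefore rest on different admission rules, and the pooled column would mix them.

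Exposure and compliance are affected too. SAP 11 sets the first OLE treatment date of former-roflumilast subjects at the parent Week 4 visit, but a never-dosed subject has no last OLE treatment date and may have no applications to count. If the Poisson model in SAP 13.1 is fitted per subject, zero exposure has no logarithm to use as offset.

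**Working it through.** The plan states no figure for this point, so there is none to reproduce. The check has three parts.

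**1. Who is in the population** (enrolled subjects, in the SAP's sense of the word)

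| Parent arm | Dosed in OLE | Protocol 6.3 | SAP 4.2 |
|---|---|---|---|
| Roflumilast | Yes | In | In |
| Roflumilast | No | Out | **In** |
| Vehicle | Yes | In | In |
| Vehicle | No | Out | Out |

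The definitions differ in one row only, and that row belongs to one former-treatment group.

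**2. Effect on TEAE percentages**

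Let p be the TEAE proportion among OLE-dosed subjects and f the never-dosed share of a column's safety population. Never-dosed subjects have no TEAEs, so

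reported percentage = p × (1 − f), and the dilution is p × f.

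Neither p nor f is in the documents, so the values below are assumptions. With p = 30%:

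| f | Former roflumilast | Former vehicle | Artefact (points) |
|---|---|---|---|
| 0.5% | 29.85% | 30.00% | −0.15 |
| 1% | 29.70% | 30.00% | −0.30 |
| 2% | 29.40% | 30.00% | −0.60 |
| 5% | 28.50% | 30.00% | −1.50 |

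Over f from 0.1% to 5% and p from 10% to 50%, the artefact runs from −0.01 to −2.50 points. For the former-roflumilast column it does not depend on the parent allocation ratio.

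The pooled column is diluted less, because its own f is smaller. As an illustration, take the planned total of about 1500 (protocol 6.2) as a single pool, assume 1:1 parent allocation, and let 1% of each group be never dosed. The former-roflumilast group has 750 subjects, 7.5 of them never dosed. The former-vehicle group contributes 750 − 7.5 = 742.5. The pooled f is 7.5 / (750 + 742.5) = 0.50%, and 30% × (1 − 0.0050) = 29.85%, a loss of about 0.15 points.

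With the protocol definition in both groups, never-dosed subjects leave both denominators and the artefact is zero for every f and p.

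**3. Effect on EAIR**

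SAP 5.5 defines EAIR as subjects with an event, divided by total exposure days in the arm, × 365.25 × 100. Take 1000 former-roflumilast subjects, f = 1%, p = 30% and 364 days of exposure for each dosed subject (all assumed).

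- Events: 0.30 × 990 = 297. Exposure: 990 × 364 = 360,360 days.
- No exposure credited to the never-dosed: 297 / 360,360 × 36,525 = 30.10 per 100 subject-years.
- 30 days credited to each of the 10 never-dosed: 297 / 360,660 × 36,525 = 30.08.

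These subjects add no events and next to no exposure, so the rate, and any difference between rates, hardly moves.

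**The case against.** **The added group may be empty.** If protocol 5.1.3 governs, nobody is enrolled without an application, and the parent-study route in SAP 4.2 adds no one. The first application is made on site at Day 1, so never-dosed enrollees should be rare in any case. The expectation of small numbers stands. The claim of emptiness does not settle the matter, because SAP 5.2, 5.3 and 6.2.1 all provide for such subjects, SAP 7.1 counts enrolled and treated subjects separately, and the SAP prevails where the documents differ. If 5.1.3 does apply, the extra clause is dead text that conflicts with those sections.

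**The wider set may be deliberate.** SAP 11 regards former-roflumilast subjects as continuing the same treatment. SAP 5.2 assigns laboratory tests, vital signs, tolerability and the depression and suicidality scales to the Primary baseline, which for these subjects goes back to the parent study. Keeping them in those summaries is coherent, so narrowing the population for every safety table would go too far. The argument does not carry over to TEAEs, for which SAP 5.2 uses the OLE baseline.

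**The planned group comparison is not distorted.** A reader might infer that unequal denominators bias the between-group difference in SAP 13.1. That difference is in EAIR, which part 3 of the working shows to be insensitive. The sections reviewed plan no difference in TEAE percentages, and SAP 5.7 plans no hypothesis tests.

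**Concealment cannot be claimed.** A reader might also infer that the change was made without disclosure. The table in SAP 3.6 is broken in the available text, and the description belonging to its third row is missing. The most that can be said is that no legible entry covers the change.

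**Conclusion.** The point holds as a minor one. SAP 4.2 departs from protocol 6.3, and under the SAP's own use of *enrolled* it admits never-dosed subjects from one former-treatment group only. TEAE percentages in the former-roflumilast and pooled columns are lowered by the factor (1 − f), always in the same direction. With f of 0.5–2% and a 30% TEAE rate in the former-roflumilast column, both assumed, that is 0.15–0.6 percentage points; the pooled column loses less. The true f is unknown and could be zero.

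The documents do not support a stronger conclusion, such as a biased EAIR contrast or a materially misleading safety profile. The case for acting is that the dilution falls on the primary endpoints, serves no analytic purpose there, and leaves exposure and compliance undefined for the subjects concerned.

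**What to change.** - In the SAP, base TEAE, EAIR, exposure and compliance summaries on subjects with at least one confirmed dose of roflumilast in ARQ-151-313, for both former-treatment groups, as in protocol 6.3.
- If the wider set is wanted for summaries that use the Primary baseline, give it a separate name and state which tables use it. Demographics, medical history and concomitant medications also use the safety population and need assigning to one set or the other.
- Enter any retained change and its reason in SAP 3.6.
- Reconcile the SAP's meaning of *enrolled* (5.2, 5.3, 6.2.1) with protocol 5.1.3.

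The cost is a short SAP edit and no new data. If both sets are kept, there is one extra population flag to program and to label in the outputs.

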4.3 Pharmacokinetic Population (PK)

The PK population includes all subjects who had a PK draw (concentration data available) post-baseline. This population will be used for the analysis of PK concentrations.

Of note, PK is only to be drawn on subjects aged 12 years or older who first enrolled under protocol amendment 1.

5 GENERAL CONSIDERATIONS

Formats and layouts of tables, listings, and figures (TLFs) will be provided in a separate document (output general layout is described in [Appendix 1](#)).

For analysis purposes, the TLFs will be summarized overall and by previous treatment group in the parent studies as indicated below. Rollovers from the ARQ-151-311/312 studies will be summarized separately from rollovers from the ARQ-151-315 study.

- Rollovers from ARQ-151-311/312 studies
 - Roflumilast cream 0.15%
 - Vehicle / Roflumilast cream 0.15%
 - Pooled Roflumilast cream 0.15%
- Rollovers from ARQ-151-315 study
 - Roflumilast cream 0.05% or 0.15%
 - Vehicle / Roflumilast cream 0.05% or 0.15%
 - Pooled Roflumilast cream 0.05% or 0.15%

 Innovaderm Research	STATISTICAL ANALYSIS PLAN, Final Version 1.0
Protocol Number: ARQ-151-313	Sponsor: Arcutis Biotherapeutics, Inc.

5.1 Sample Size

Up to approximately 1500 subjects that have completed the 4-week treatment period in studies ARQ-151-311, ARQ-151-312, or ARQ-151-315 and are willing and qualified to enroll in this long-term extension study will receive roflumilast cream 0.15% (ARQ-151-311/312 roll-overs) or roflumilast cream 0.05% (ARQ-151-315 roll-overs) QD.

The sample size will provide a sufficient number of subjects to evaluate the long-term safety of roflumilast cream 0.15% or roflumilast cream 0.05% over 24 or 52 weeks of treatment (Cohort-Week 24 and Cohort-Week 52, respectively).

5.2 Baseline

There are two baseline definitions for the analyses:

- Primary baseline is defined as the last observation before or on the first dose of roflumilast cream 0.15% or 0.05% in ARQ-151 parent studies for subjects administered roflumilast previously and before or on the first dose of roflumilast cream 0.15% or 0.05% in this study* for subjects administered vehicle previously.
- OLE baseline is defined as the last observation before or on the first dose of roflumilast cream 0.15% or 0.05%* in this study.

If the last non-missing assessment was performed on the same date as the first dose of roflumilast cream* and time is not available, the assessment will be considered as baseline, except for adverse events (AEs) and medications starting on the first dose date which will be considered post-baseline. For subject local tolerability assessments, if the last non-missing assessment was performed on the same date as the first dose of roflumilast cream*, the assessment will be considered as baseline, regardless of the time of the assessment.

For the subjects administered vehicle in the parent study, the definition for Primary and OLE baselines are the same.

* Enrollment date (usually the Week 4 visit in the parent study) for enrolled subjects who discontinued early from this study before the first application of roflumilast cream 0.15% or 0.05%.

The following table ([Table 2](#)) described the baseline used in the analysis:

 Innovaderm Research	STATISTICAL ANALYSIS PLAN, Final Version 1.0
Protocol Number: ARQ-151-313	Sponsor: Arcutis Biotherapeutics, Inc.

Table 2 Summary of Primary/OLE Baseline in the Analyses

Analyses	Baseline*
Demographics and Baseline Characteristics	Primary baseline and OLE baseline, as applicable
Efficacy Analysis	Primary baseline and OLE baseline
Safety analysis for AEs and concomitant medications	OLE baseline
Safety analysis for clinical laboratory, vital signs, local tolerability assessments. PHQ-8, Modified PHQ-A, CDI-2, C-SSRS, and physical examination	Primary baseline

* Refer to Section 8 for more details.

